2.2 Study Design Overview

[figure not shown]
This is a Phase 2, multicenter, randomized, double-blind, parallel-group, placebo-controlled dose ranging study that will evaluate the safety and efficacy of cedirogant in approximately 200 adult subjects with moderate to severe plaque psoriasis and who are candidates for systemic therapy or phototherapy.

The study is comprised of a 28-day Screening Period, a 16-week double-blind Treatment Period, and a 30-day Follow-up Period.

The schematic of the study is shown in [Figure 1](#).

This study was terminated early by AbbVie due to preclinical findings in the cedirogant 39-week dog toxicity study. The interim analysis pre-defined in the protocol will not be conducted. The final database lock will occur after the last on-going subject completes the follow-up phone call or withdraws from the study.

Figure 1. Study Schematic

PASI = Psoriasis Area Severity Index; PBO = placebo; QD = once daily

2.3 Treatment Assignment and Blinding

All subjects will be assigned a unique identification number by the IRT at the screening visit. For subjects who rescreen, the screening number assigned by the IRT at the initial screening visit should be used. The IRT will assign a randomization number that will encode the subject's treatment group assignment according to the randomization schedule.

Subjects who meet eligibility criteria at Baseline will be randomized in a 1:1:1:1 ratio to 1 of the 4 treatment groups:

- Cedirogant 375 mg once daily (QD) (N = 50)
- Cedirogant 150 mg QD (N = 50)
- Cedirogant 75 mg QD (N = 50)

- Placebo QD (N = 50)

All active and placebo treatment will be taken orally (cedirogant 75 mg tablets and matching placebo). There is no stratification factor for the randomization.

2.4 Sample Size Determination

Given the planned total sample size of 200 subjects (50 subjects in each arm), the study has more than 95% power to detect the treatment differences of 60% in PASI 75 in at least one cedirogant group versus placebo (PASI 75 response rate of 11%) using a two-sided significance level of 0.1 based on the 2-sample Chi-Squared test.

3.0 Endpoints

3.1 Primary Endpoint

The primary endpoint is the achievement of $\geq 75\%$ reduction from baseline in PASI score (PASI 75) at Week 16.

3.2 Secondary Endpoints

The secondary endpoints are:

- Achievement of a static Physician Global Assessment (sPGA) score of clear or almost clear at Week 16
- Achievement of $\geq 50\%$ reduction from baseline in PASI score (PASI 50) at Week 16
- Achievement of $\geq 90\%$ reduction from baseline in PASI score (PASI 90) at Week 16
- Achievement of 100% reduction from baseline in PASI score (PASI 100) at Week 16
- Achievement of Psoriasis Symptoms Scale (PSS) total score of 0 at Week 16 for subjects with PSS >0 at Baseline
- Achievement of itch Numerical Rating Scale (NRS) ≥ 4 -point improvement from Baseline at Week 16 for subjects with itch NRS ≥ 4 at Baseline

3.3 Other Efficacy Endpoints

Additional efficacy endpoints include the primary and all secondary endpoints assessed at visits other than the Week 16 Visit as noted in the Study Activities table (Appendix D of the protocol). Additional efficacy endpoints include the following measurements assessed at visits as specified in the Study Activities table:

- Change from baseline in Dermatology Life Quality Index (DLQI) score
- Achievement of a DLQI score of 0 or 1
- Achieving a change of ≥ 4 points from baseline in DLQI score (for patients whose DLQI score at baseline is ≥ 4)
- Treatment Satisfaction Questionnaire for Medication Version 9 (TSQM-9) domain scores (effectiveness, convenience and global satisfaction domains)
- Change from baseline in Hospital Anxiety and Depression Scale (HADS)-Anxiety score
- Change from baseline in HADS-Depression score
- Change from Baseline in Work Productivity and Activity Impairment (WPAI): Psoriasis Questionnaire measures:
 - Percent work time missed (Absenteeism)
 - Percent impairment while working (Presenteeism)
 - Percent overall work impairment
 - Percent activity impairment

3.4 Safety Endpoints

Safety evaluations include AE monitoring, physical examinations, vital sign measurements, electrocardiogram (ECG) variables, and clinical laboratory testing (hematology, chemistry, and urinalysis) as measures of safety and tolerability for the entire study duration.

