### 3.5 Safety Measures

---

Safety evaluations include AE monitoring, physical examinations, vital sign measurements, electrocardiogram (ECG) variables, and clinical laboratory testing (hematology, chemistry, and urinalysis) as measures of safety and tolerability for the entire study duration.

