10.0 Safety Analyses

10.1 General Considerations

Safety data will be summarized for the Safety Population. Safety summaries will be presented by treatment group, including a total group for all subjects on active study drug. For the safety analysis, subjects are assigned to a treatment group based on the treatment actually received, regardless of the treatment randomized.

The overview of TEAEs, and potentially clinically important (PCI) findings in laboratory variables and vital sign variables will also be summarized among the Safety Populations.

Missing safety data will not be imputed.

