10.4 Analysis of Vital Signs

Vital sign measurements of systolic and diastolic blood pressure will be summarized.

The raw value of each vital sign variable and change from baseline at each time point will be summarized by treatment group with number of subjects, mean, standard deviation, median, minimum and maximum. The 95% CI based on normal approximation will be provided for the mean change from baseline.

Vital sign variables will be evaluated based on potentially clinically important (PCI) criteria ([Appendix C](#)) among the Safety Population. For each vital sign PCI criterion, the number and percentage of subjects who have a vital sign value meeting the criteria will be summarized. Listings will be provided to summarize subject-level vital sign data for subjects meeting PCI criteria.

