10.6 Other Safety Analyses

There will be no other safety analyses for this study.

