11.0 Other Analyses

There will be no other analyses for this study.

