MACE	There is an increased risk of cardiovascular disease in the psoriasis patient population.	Other Ischaemic heart disease SMQ_narrow Central nervous system hemorrhages and cerebrovascular conditions SMQ_narrow Myocardial infarction SMQ_narrow Death and Sudden Death - HLT	No	Yes	None

Safety Topic of Interest	Basis for Inclusion	Criteria for Identification of Event	Are events adjudicated (yes/no)? If yes, external or internal adjudication?	Special Collection Forms or Safety Studies	Relevant Restrictions [#]
Ocular events	In a healthy volunteer study of an ROR γ t compound related to ABBV-157, 3 of 9 subjects developed eye related events after multiple doses, including one subject who was seen by eye specialists and required prolonged treatment with steroid eye drops and an oral NSAID (aspirin-like drug).	Conjunctival disorders SMQ_narrow Corneal disorders SMQ Scleral disorders SMQ_narrow	No	Yes	Current phase 2b protocol requires any subject with CTCAE Grade 2 or higher AE ocular event must follow up with an ophthalmologist within 7 days. Grade 2 or higher ocular AEs considered related to study drug administration qualify for withdrawal criteria.
Possible malignancies	Comorbidity with patient population, NMSC most common. Theoretical possibility of decreased immune surveillance against malignancies with alteration of immune pathways.	- Malignant tumours SMQ - narrow	No	No	Exclusion of subjects with a history of any malignancy within the last 5 years or documented active malignancy except for successfully treated non-melanoma skin cancer (NMSC) or localized carcinoma in situ of the cervix.
Non-melanoma skin cancer (NMSC)	Comorbidity with patient population, NMSC most common. Theoretical possibility of decreased immune surveillance against malignancies with alteration of immune pathways.	Skin malignant tumours SMQ Broad excluding preferred terms identified by the Melanoma CMQ	No	No	Exclusion of subjects with a history of untreated non-melanoma skin cancer (NMSC).

Safety Topic of Interest	Basis for Inclusion	Criteria for Identification of Event	Are events adjudicated (yes/no)? If yes, external or internal adjudication?	Special Collection Forms or Safety Studies	Relevant Restrictions [#]

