Appendix C. Potentially Clinically Important Criteria for Safety Endpoints

The criteria for Potentially Clinically Important (PCI) laboratory findings are described in Table C-1 and Table C-2, and the PCI criteria for vital sign findings are described in Table C-3.

Table C-1. Criteria for Potentially Clinically Important Hematology Values

Hematology Variables	Units	Definition of Potentially Clinically Important NCI CTCAE (Version 4.03) Grade 3 or greater
		Very Low
Hemoglobin	g/dL	< 8.0
Platelets count	10 ⁹ /L	< 50.0
WBC count	10 ⁹ /L	< 2.0
Neutrophils	10 ⁹ /L	< 1.0
Lymphocytes	10 ⁹ /L	< 0.5

Note: A post-baseline value must be more extreme than the baseline value to be considered a potentially clinically important finding.

Table C-2. Criteria for Potentially Clinically Important Chemistry Values

Chemistry Variables	Units	Definition of Potentially Clinically Important NCI CTCAE (Version 4.03) Grade 3 or greater	
		Very Low	Very High
TBL	mcmol/L		$> 3.0 \times \text{ULN}$
ALP	U/L		$> 5.0 \times \text{ULN}$
SGOT/AST	U/L		$> 5.0 \times \text{ULN}$
SGPT/ALT	U/L		$> 5.0 \times \text{ULN}$
Albumin	g/L	< 20	
Glucose	mmol/L	< 2.2	> 13.9
Triglycerides	mmol/L		> 5.7
Creatinine	mcmol/L		$> 3.0 \times \text{ULN}$ $(> 3.0 \times \text{BL})$
Sodium	mmol/L	< 130	> 155
Potassium	mmol/L	< 3.0	> 6.0
Calcium	mmol/L	< 1.75	> 3.1
CPK	U/L		$> 5.0 \times \text{ULN}$
Total Cholesterol	mmol/L		> 10.34
GGT			$> 5.0 \times \text{ULN}$

Note: A post-baseline value must be more extreme than the baseline value to be considered a potentially clinically important finding.

Table C-3. Criteria for Potentially Clinically Important Vital Sign Values

Vital Signs Variables	Criterion	Definition of Potentially Clinically Important
Systolic Blood Pressure (mmHg)	Low	Value ≤ 90 mmHg and decrease ≥ 20 mmHg from Baseline
	High	Value ≥ 160 mmHg and increase ≥ 20 mmHg from Baseline
Diastolic Blood Pressure (mmHg)	Low	Value ≤ 50 mmHg and decrease ≥ 10 mmHg from Baseline
	High	Value ≥ 100 mmHg and increase ≥ 10 mmHg from Baseline

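### SAP 3.4 names ECG variables as a safety endpoint, but no section of the SAP analyses them, so no ECG values or QTcF counts will be reported by treatment group

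*SAP*

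**What the plan says.** SAP 3.4 (Safety Endpoints) reads: "Safety evaluations include AE monitoring, physical examinations, vital sign measurements, electrocardiogram (ECG) variables, and clinical laboratory testing". Protocol 3.5 (Safety Measures) gives the same list: "electrocardiogram (ECG) variables, and clinical laboratory testing (hematology, chemistry, and urinalysis) as measures of safety and tolerability for the entire study duration".

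The analysis text is narrower. SAP 10.1 says that "potentially clinically important (PCI) findings in laboratory variables and vital sign variables will also be summarized among the Safety Populations", and Appendix C follows that scope: Tables C-1 and C-2 are for laboratory values, and "the PCI criteria for vital sign findings are described in Table C-3". The vital signs section, SAP 10.4, is about blood pressure only: "Vital sign measurements of systolic and diastolic blood pressure will be summarized".

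Two closing statements follow. SAP 10.6: "There will be no other safety analyses for this study". SAP 11.0: "There will be no other analyses for this study".

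The protocol uses the ECG for decisions about individual subjects. Eligibility criterion 19 (protocol 5.1) sets QTcF limits at Screening and Baseline. Protocol 5.5 lists, among the reasons for discontinuation, a confirmed QTcF above 500 msec or a confirmed change from baseline above 60 msec. Protocol 7.6 names adverse events, laboratory assessments and vital signs for summary, does not name ECG, and leaves the detail to the SAP.

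**The concern.** Safety is part of the primary objective, and the comparison is with placebo. Something the SAP calls a safety endpoint should therefore have a stated analysis by treatment group. For ECG there is none, and the closing statements in 10.6 and 11.0 mean the gap cannot be read as detail to be filled in later.

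What would be lost is the between-arm view of the ECG data: mean QTcF and its change by visit, and the number of subjects in each arm who crossed the protocol's own QTcF limits. ECG findings would be seen only incidentally:

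- as adverse events by preferred term (SAP 10.2.3);
- as adverse events leading to discontinuation (10.2.5);
- as discontinuation reasons (5.0);
- within the deviation category for subjects who met withdrawal criteria but stayed in (Appendix A), which does not separate QTcF from other criteria.

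None of these reports an ECG value or a QTcF count.

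**Working it through.** There is no figure in the plan to reproduce. The check sets the list in SAP 3.4 against everything in the SAP that could produce an ECG output.

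**Evaluation types against analysis sections**

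| Named in SAP 3.4 | Analysis in SAP Section 10 |
|---|---|
| Adverse events | 10.2 |
| Laboratory tests | 10.3 |
| Vital signs | 10.4 (blood pressure) |
| ECG variables | none |
| Physical examinations | none |

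With an analysis: 3 of 5. Without: 5 − 3 = 2.

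**Data that will be collected** (protocol Appendix D). A single 12-lead ECG is ticked at Screening, Baseline and Weeks 2, 4, 6, 8, 12 and 16, which is 8 planned visits for a subject who completes. Two are before dosing, so 8 − 2 = 6 are after the first dose. With the Premature Discontinuation column the total is 8 + 1 = 9 columns.

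**Criteria in SAP Appendix C.** Hematology (C-1) has 5 variables, chemistry (C-2) has 14 and blood pressure (C-3) has 2. 5 + 14 + 2 = 21, of which 0 are ECG variables.

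**Topics in SAP Appendix B.** The printed list has 13: serious infection, GI motility, herpes zoster, opportunistic infection, active tuberculosis, hepatic disorders, lymphopenia, anemia, MACE, ocular events, possible malignancies, non-melanoma skin cancer, and other malignant tumours. None is an ECG, QT or arrhythmia topic. The nearest is MACE. Its searches are ischaemic heart disease, cerebrovascular conditions and "Myocardial infarction SMQ_narrow Death and Sudden Death - HLT". SAP 10.2.6 says the final list follows a product-level safety plan that is not among the documents. That plan governs topics found by searching adverse event terms, so on the text of 10.2.6 it would not supply summaries of measured ECG values.

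**Is the gap a result of early termination?** The documents do not say. The SAP version history ties the loss of efficacy testing and of the interim analysis to termination. For Section 10.3 it records an AST eDISH plot added and shift tables dropped. It records no removal of an ECG analysis. Version 2.0 still keeps by-visit summaries by arm for laboratory data and blood pressure.

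**Is text missing?** SAP Sections 10.1 to 10.6 and Appendices A to C run without a break, so the absence is not due to removed pages.

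**The case against.** The strongest reply is that the SAP delivers what protocol 7.6 asks for: adverse events, laboratory data and vital signs. On that reading SAP 3.4 is a list of assessments carried over from protocol 3.5, where the heading is Safety Measures. The equal silence on physical examinations supports this. The mismatch would then be one of wording.

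Several facts also lower the stakes:

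- The ECGs are single recordings listed under local examinations, at about 50 sites. They suit individual monitoring better than estimation of small mean QTcF differences. No central reading is described in the documents reviewed.
- A dedicated study in healthy volunteers (protocol 2.2) found mean placebo-corrected QTcF changes of 4 msec at 375 mg, this trial's top dose, and 6 msec at 750 mg. The protocol judged that these were not clinically relevant.
- The DMC reviews unblinded ECG results under its own charter (protocol 5.10).
- Cardiac events trigger supplemental forms, including one for arrhythmia (protocol 6.1).
- The trial stopped early, and the number randomized is not given.

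Most of this stands, and it limits the consequence. It does not close the gap. DMC review is monitoring during the study, and its outputs are not known from these documents. Adverse event tables depend on the investigator reporting an event, and they carry no QTcF values. The QT study was in healthy volunteers, whereas this trial has placebo-controlled ECGs in patients over up to 16 weeks. If SAP 3.4 was meant only as a list of assessments, its heading says otherwise, and the SAP should state the intention.

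**Conclusion.** The concern holds. SAP 3.4 names ECG variables as a safety endpoint, Section 10 and Appendix C contain no ECG analysis, and 10.6 and 11.0 exclude one. Against six scheduled post-dose ECGs per completing subject, plus one at premature discontinuation, the SAP plans no summary by visit, no change from baseline, no QTcF threshold count and no ECG listing.

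This should be corrected, but it is a gap in reporting. It does not threaten the trial's conduct, and nothing here suggests a QT effect. No trial-level total of affected ECGs can be given without the number randomized. Physical examinations share the same mismatch. The point is confined to ECG because the protocol attaches numeric QTcF limits to it. The absence is certain from the text. Whether the full remedy is feasible depends on which ECG fields were entered in the database, which the documents do not show.

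**What to change.** Add an ECG subsection to SAP Section 10, for the Safety Population:

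1. Summarize QTcF, and any other ECG variable recorded as a number, as value and change from baseline by visit and treatment group, with the descriptive statistics already used in 10.3 and 10.4.
2. Give the number and percentage of subjects in each treatment group, with a listing, who meet each QTcF criterion of protocol 5.5 as worded there: confirmed value above 500 msec; confirmed change from baseline above 60 msec.
3. Because the scheduled ECG is single, cite where confirmation is defined. If unconfirmed single readings are also counted, label them and show them separately.

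With a subsection of its own for ECG, the statement in 10.6 can stay as it is.

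If the sponsor prefers listings only, or no ECG output, the SAP should say so, and 3.4 should be reconciled with Section 10 for both ECG and physical examinations.

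The cost of the preferred change is some SAP text, one or two tables and a listing, with no new data collection. This assumes that QTcF is held as a number. That is plausible, since criterion 19 and protocol 5.5 both need a QTcF value, but it is not shown. If it is not held as a number, only a listing or a categorical summary is possible. The alternative costs a sentence or two.

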4.0 Analysis Populations

The following population sets will be used for the analyses.

The Intent-to-Treat (ITT) Population includes all randomized subjects. The efficacy analyses, summary of demographic, and baseline disease characteristics will be carried out with the ITT Population. Subjects will be analyzed as randomized.

The Safety Population includes all subjects who are randomized and received at least 1 dose of study drug. All safety analyses will use the Safety Population. Subjects will be analyzed as treated (i.e., according to the actual treatments received), regardless of the treatment assigned. The 'as-treated' treatment group is determined by the treatment the subject received during the majority of the subject's drug exposure time in the analysis period.

5.0 Subject Disposition

The number of subjects for each of the following categories will be summarized, for overall and for each group in ITT Population:

- Subjects randomized;
- Subjects who took at least one dose of study drug;
- Subjects who completed study;
- Subjects who completed study drug;
- Subjects who prematurely discontinued study drug;
- Subjects who prematurely discontinued study.

Number and percentage of subjects who discontinue study drug or who discontinue from study will be summarized by primary reason for each treatment group and overall.

In addition, the above summaries (except for the reason for premature discontinuation) will also be summarized by center in the accountability table.

6.0 Study Drug Duration and Compliance

For the Safety population, duration of treatment will be summarized for each treatment group and for all active investigational study drug dose groups combined. Duration of treatment is defined for each subject as last dose date minus first dose date +1. Duration of treatment will be summarized using the number of subjects treated, mean, standard deviation, median, minimum and maximum. In addition, the number and percentage of subjects in each treatment duration interval (≥ 1 dose, ≥ 4 weeks, ≥ 12 weeks, ≥ 16 weeks) will be summarized.

Treatment compliance in the treatment period will be summarized by treatment group based on the Safety population. Treatment compliance for each subject is defined as the number of tablets actually taken divided by the number of tablets that should have been taken. For subjects who prematurely discontinued the study drug, the planned tablets will only be counted prior to that scheduled visit of discontinuation. The compliance rate will be summarized by treatment group.

7.0 Demographics, Baseline Characteristics, Medical History, and Prior/Concomitant Medications

Demographics, baseline or disease characteristics, medical history, and prior and concomitant medications will be summarized for the ITT population overall and by treatment group. Categorical variables will be summarized with the number and percentage of subjects; percentages will be calculated based on the number of non-missing observations. Continuous variables will be summarized with descriptive statistics (number of non-missing observations, mean and standard deviation, median, minimum and maximum).

7.1 Demographics and Baseline Characteristics

Continuous demographic variables include age, weight, height, and body mass index (BMI). Categorical demographic variables include sex, ethnicity, race, age (< 40, 40 – 65), weight (< 100 or ≥ 100 kg), BMI (< 25 or ≥ 25 kg/m²), region (North America,

rest of world), tobacco user (current, former, never, unknown), and alcohol user (current, former, never, unknown).

Disease characteristics include the following: Baseline PASI, Baseline sPGA, Baseline PSS, Baseline BSA, Baseline NRS, Baseline DLQI, Baseline HADS, Baseline WPAI, history of psoriatic arthritis, prior biologic and disease duration in years as a continuous and categorical (< 5 or \geq 5 years) variable.

7.2 Medical History

Medical history data will be coded using the Medical Dictionary for Regulatory Activities (MedDRA). The actual version of the MedDRA coding dictionary will be noted in the statistical tables and clinical study report. The number and percentage of subjects in each medical history category (by MedDRA system organ class and preferred term) will be summarized overall and by treatment group. The system organ class (SOC) will be presented in alphabetical order, and the preferred terms will be presented in alphabetical order within each SOC. Subjects reporting more than one condition/diagnosis will be counted only once in each row (SOC or preferred term).

7.3 Prior and Concomitant Medications

Prior and concomitant medications will be summarized by generic name. A prior medication is defined as any medication taken prior to the date of the first dose of study drug. A concomitant medication is defined as any medication that started prior to the date of the first dose of study drug and continued to be taken after the first dose of study drug or any medication that started on or after the date of the first dose of study drug, but not after the date of the last dose of study drug. The number and percentage of subjects taking medications will be summarized by generic drug name based on the World Health Organization (WHO) Drug Dictionary for both prior and concomitant medications.

